2.11. SAFETY: SAEs AND TOXICITIES

Following the criteria established in the protocol, "Any patient included in the study and who has received at least a single dose of study medication will be evaluable for toxicity analyzes."

GEIS-30 STUDY

Statistical analysis plan

AES and Toxicities Table 74. All monitoring

		Cohort A	Cohort B	Total	p-value
		N (%)	N (%)	N (%)	
AE	Yes				
	Total				
	<hr/>				
toxicity (related)	No				
	Yes				
	Total				
<hr/>					
≥3 AE grade	No				
	Yes				
	Total				
<hr/>					
toxicity grade ≥3 (related)	No				
	Yes				
	Total				
<hr/>					
SAE (at least one per patient) ³	No				
	Yes				
	Total				

1: Chi-square; 2: Fisher's exact test; 3: patients could present more than one SAE

Table 75. AEs and Toxicities with start date prior to treatment

		Cohort A	Cohort B	Total	p-value
		N (%)	N (%)	N (%)	
AE	No				
	Yes				
	Total				
<hr/>					
AE grade ≥ 3	No				
	Total				

1: Chi-square; 2: Fisher's exact test

Table 76. AEs and Toxicities during treatment

		Cohort A	Cohort B	Total	p-value
		N (%)	N (%)	N (%)	
AE	Yes				
	Total				
<hr/>					
Toxicity (related)	No				
	Yes				
	Total				
<hr/>					
AE grade ≥3	No				
	Yes				
	Total				
<hr/>					
Toxicity grade ≥3 (related)	No				
	Yes				
	Total				

1: Chi-square; 2: Fisher's exact test

Table 77. ESA and Toxicities after treatment

		Cohort A	Cohort B	Total	p-value
		N (%)	N (%)	N (%)	
AE	No				
	Yes				
	Total				

GEIS-30 STUDY

Statistical analysis plan

Toxicity (related)	No
	Yes
	Total
AE grade ≥ 3	No
	Yes
	Total
Toxicity grade ≥ 3 (related)	No
	Total

1: Chi-square; 2: Fisher's exact test

Table 78. AE and Toxicities with no known date

		Cohort A	Cohort B	Total	p-value
		N (%)	N (%)	N (%)	
AE	No				
	Yes				
	Total				
Toxicity (related)	No				
	Yes				
	Total				
AE grade ≥ 3	No				
	Yes				
	Total				
Toxicity grade ≥ 3 (related)	No				
	Total				

1: Chi-square; 2: Fisher's exact test

The frequencies of all toxicities with grade ≥ 3 are presented below.

Table 79. Frequencies of AEs grade ≥ 3

	Cohort A	Cohort B	Total
	N (%)	N (%)	N (%)
Abscess of tumor mass - Grade 3			
ALT increased - Grade 3			
Anemia - Grade 3			
Ascites - Grade 3			
AST increased - Grade 3			
Asthenia - Grade 3			
Back pain - Grade 3			
Bilirubin increased - Grade 3			
Cardiac dysrhythmia / chest pain - Grade 3			
Diarrhea - Grade 3			
Fatigue - Grade 3			
Femur fracture - Grade 3			
Gastrointestinal bleeding - Grade 5			
General Status deterioration - Grade 5			
Ggt increased worsening - Grade 3			
Hypertension - Grade 3			
Hyporexia - Grade 3			
Muscle weakness - Grade 3			
Myocardial infarction - Grade 3			
Nausea - Grade 3			
Neutropenia - Grade 3			

GEIS-30 STUDY

Statistical analysis plan

Pain - Grade 3

Toothache - Grade 3

Vomiting - Grade 3

The frequencies of all (related) treatment toxicities with grade ≥ 3 .

Table 80. Frequencies of (related) toxicities grade ≥ 3

	Cohort A	Cohort B	Total
	N (%)	N (%)	N (%)
ALT increased - Grade 3			
AST increased - Grade 3			
Asthenia - Grade 3			
Bilirubin increased - Grade 3			
Diarrhea - Grade 3			
Hypertension - Grade 3			
Muscle weakness - Grade 3			
Myocardial infarction - Grade 3			
Nausea - Grade 3			
Neutropenia - Grade 3			
Vomiting - Grade 3			

GEIS-30 STUDY

Statistical analysis plan

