## **9.2. Reporting of Adverse Events**

The sponsor will collect AEs up to 30 days after administration of the last dose of study drug.

All adverse events must be recorded using medical terminology in the source document and the CRF. Investigators must assess the severity (grade) of the event following NCI-CTCAE V 4.0 Criteria and assign a relationship to study therapy and pursue and obtain information adequate both to determine the outcome and to assess whether it meets the criteria for classification as a SAE requiring immediate notification. The investigator must provide any information as requested by sponsor in addition to that on the CRF.

Any serious adverse events which occur from patient informed consent signature, during the clinical study or within 30 days of receiving the last dose of study medication, whether or not related to the study drug, must be reported by the investigator. In addition, any SAEs which occur as a result of protocol specific diagnostic procedures or interventions must also be reported. Beyond this period of time, only those SAEs suspected to be related to the study drug will be reported.

All SAEs suspected to be related to study treatment should be followed after the treatment/study withdrawal until the event or its symptoms have resolved or stabilized at a

grade acceptable to the Investigator, Chief investigator and/or Sponsor.

Site investigation staff should notify the sponsor, all the pregnancies of female subjects and female partners of male subject that occurred during the clinical trial within 24 hours from becoming aware. Site investigation staff, should also communicate the outcome of the pregnancy within 24 hours since the awareness.

The cause of death of a deceased patient in a clinical trial, whether the case of an expected event or associated with the investigational agent, is considered an SAE and therefore must be communicate using the SAE form. The autopsy report should be sent to Sponsor identified only with the patient inclusion number.

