### **Safety profile (according CTCAE, version 4.0)**

The safety and tolerability of Pazopanib will be determined by means of type, incidence, severity, timing, seriousness, and relatedness; of reported AEs, physical examinations, and laboratory tests. Toxicity will be graded and tabulated by the NCI-CTCAE v 4.0.

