### **10.3. Safety assessment**

Any patient included in the study receiving at least a single dose of study medication will be evaluable for the toxicity analysis.

Safety profile will be characterized by treatment-emergent Adverse Events (TEAE), vital signs and laboratory abnormalities. Assessment of adverse events will include type, incidence, severity (graded by the National Cancer Institute [NCI] Common Terminology Criteria for Adverse Events [CTCAE], Version 4.0), timing, seriousness, and relatedness; and laboratory abnormalities. Baseline tumor-related signs and symptoms will be recorded as adverse events during the trial if they worsen in severity or increase in frequency.

In each study visit all adverse events will be registered according to NCI-CTC version 4.0

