1.16. OBJECTIVES OF THE STUDY

1.16.1. Primary objective

The objective of this study is to evaluate the activity of Pazopanib in patients with advanced and / or metastatic liposarcoma by means of progression-free survival (PFS) determined after 12 weeks of treatment (according to the RECIST criteria v1.1 and central radiological revision).

1.16.2. Secondary objectives:

- Median progression-free survival (median PFS).
- Objective tumor response [Complete confirmed response (CR) and partial response (PR) defined by RECIST 1.1].
- Time to start of response.
- Duration of response.
- Overall survival (OS).
- Clinical benefit rate (CBR).
- Growth modulation index (GMI).
- Security profile (according to CTCAE, version 4.0).

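### SAP 2.11 has no step coding adverse events to CTCAE v4.0 terms and Table 79 uses labels that appear uncoded, so per-term rates of severe events may be wrong in either direction

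*SAP*

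**What the plan says.** **Protocol.** The safety endpoint in 10.1.2 states: "Toxicity will be graded and tabulated by the NCI-CTCAE v 4.0". Section 10.3 adds: "In each study visit all adverse events will be registered according to NCI-CTC version 4.0". Section 9.2 governs what the site writes down: "All adverse events must be recorded using medical terminology in the source document and the CRF". In that section CTCAE is named for the severity grade only.

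**SAP.** Section 1.16.2 repeats CTCAE v4.0 as the standard for the safety objective. Section 2.11, which specifies the safety tables, names no dictionary, no coding step and no rule for grouping terms. Table 79 (all events of grade 3 or higher) and Table 80 (related events of grade 3 or higher) are shells with row labels already filled in and all counts blank. Labels in Table 79 include "Cardiac dysrhythmia / chest pain - Grade 3", "Ggt increased worsening - Grade 3", "Abscess of tumor mass - Grade 3" and "General Status deterioration - Grade 5". Asthenia and Fatigue each have their own row. Neither table says whether N counts patients or events, or that a patient is counted once per term.

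Tables 74 and 76 give yes/no counts of patients with any grade ≥3 event and any related grade ≥3 toxicity, whatever the term.

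**The concern.** Sites may record events in ordinary medical language, while the protocol wants the tables organised by CTCAE. Something has to turn the one into the other, and the SAP does not say what. Several Table 79 labels look as if recorded text has passed straight into the table.

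That can distort a per-term rate in two ways. A row that joins two events gives no rate for either one, and overstates a term if it is read as that term's rate. Two rows that hold one toxicity under different words can each show less than its true rate. In the text available, Tables 79 and 80 are the only tables that give severe events by type, so the totals elsewhere cannot correct an error in a single term.

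**Working it through.** There is no figure in the plan to reproduce. The check compares the protocol rule with the row labels, followed by an illustration of size.

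**1. Row count.** Table 79 has 24 distinct labels, 22 fixed at Grade 3 and 2 at Grade 5. Table 80 has 11 distinct labels, all of which also appear in Table 79.

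**2. Labels against the rule.**

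| Table 79 label | What it shows | In Table 80? |
|---|---|---|
| Cardiac dysrhythmia / chest pain | Two events on one line; a patient with only one of them has no row for that event alone | No |
| Ggt increased worsening | Two descriptions of change in one label | No |
| Abscess of tumor mass; General Status deterioration | Descriptive wording that appears uncoded | No |
| Asthenia; Fatigue | Two rows that may be one toxicity | Asthenia only |

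The first row shows merging and the last shows possible splitting. Both would follow from a missing coding step, and they push rates in opposite directions.

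**3. Size of a split (assumed counts).** Let *a* and *b* patients stand in two synonymous rows out of *N*. The rows read *a/N* and *b/N*. The combined rate lies between max(*a*,*b*)/*N*, if the patients are the same, and (*a*+*b*)/*N*, if they are all different. Take *N* = 37, the maximum per cohort (Protocol 1.16, SAP 1.13.1):

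| Assumed a, b | Each row | Combined rate |
|---|---|---|
| 1, 1 | 1/37 = 2.7% | 2.7% to 2/37 = 5.4% |
| 2, 2 | 2/37 = 5.4% | 5.4% to 4/37 = 10.8% |
| 3, 3 | 3/37 = 8.1% | 8.1% to 6/37 = 16.2% |

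For two equal rows the shortfall is at most a factor of 2. It is nil if the same patients are in both.

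**4. Size of a merge (assumed counts).** If 1 patient had only a dysrhythmia and 1 other had only chest pain, the joint row reads 2/37 = 5.4%, while each event has a rate of 1/37 = 2.7%. Here the row is too high for either term.

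**5. What is untouched.** Tables 74 and 76 classify patients by whether they had any grade ≥3 event, so regrouping terms leaves them unchanged. The decision rules in Protocol 10.4 count 12-week successes and use no per-term event rate.

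**The case against.** The strongest reply is that the protocol sentence can be read as tabulation by CTCAE grade, which Tables 79 and 80 do, and that 10.3 implies classification at entry, so no later coding step is needed. This carries some weight, but it does not explain the table. If events were registered by CTCAE term, a row with two events joined by a slash, or one reading as both increased and worsening, would not be expected.

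A second reply is that the SAP is visibly a translation from Spanish, so odd labels may be artefacts. That is plausible for the general-status label. It does not account for the joined cardiac row. The labels therefore appear uncoded, but are not proved to be so.

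A reader might also infer more than the documents support:

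- **That severe toxicity is shown to be understated.** Every cell is blank, the same patients may be in both rows, and the cardiac row shows merging rather than splitting.
- **That Table 80 also splits one toxicity.** It has none of the descriptive or joined rows above, and Asthenia without Fatigue. It shares only the missing coding rule.
- **That muscle weakness belongs with asthenia, or back pain with pain.** Neither document reproduces the CTCAE term list, so this cannot be settled here. Asthenia and Fatigue are a plausible pair for the same reason, not a confirmed one.
- **That an event at another grade has no line.** The labels may simply list the combinations seen so far, and nothing says that the list is closed.

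SAP Annex II, a listing of related toxicities, is in the contents list but its body is not in the text available. It is not counted as missing here.

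**Conclusion.** The point holds in a limited form. The protocol requires tabulation by NCI-CTCAE v4.0. SAP 2.11 provides no coding step, and Table 79 contains one row that merges two events, one that mixes two descriptions, and a pair that may be one toxicity. If the shell is filled in as it stands, the rates of individual severe events may be wrong in either direction.

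The size cannot be derived from the documents. In the illustration of 2 patients in each of two synonymous rows, the combined rate is 5.4% to 10.8% against 5.4% shown in each row. This rests on assumed counts, on 37 patients in the cohort, and on the two labels being one CTCAE term. The overall grade ≥3 rates in Tables 74 and 76 stand, as do the efficacy conclusions. The departure affects a secondary safety output and is worth correcting because it goes against a stated protocol rule and is cheap to repair.

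**What to change.** Add to SAP 2.11 that every adverse event is coded to a CTCAE v4.0 term before tabulation, and that a combined entry is split into separate events, each with its own grade and relationship to treatment. Build the rows of Tables 79 and 80 from the coded terms rather than from pre-filled text. Count each patient once per term at worst grade, with columns for grades 3, 4 and 5, and state that N is patients. Keep the verbatim wording in a listing, so that the coding can be traced.

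The cost is a small amount of coding work (Table 79 has 24 labels at present) and two revised shells. No new data are needed. A combined entry such as the cardiac row may need a query to the site to establish which event or events occurred.

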3. APPENDIX I: EFFICACY ACCORDING TO GMI

3.1. ENDPOINT MAIN ACCORDING TO GMI

In the sections presented below, the possible relationship between the main efficacy variables and the categorized GMI variables is analyzed: <1, 1-1.33 and> 3 (see Table 69. Growth modulation index (GMI) (ITT) and Table 71. Modulation index Growth (GMI) (PP).

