##### **Growth Modulation Index (GMI)**

GMI is the ratio between time to progression (TTP) with pazopanib (TTPp) divided by the

TTPp-1 with the previous line of therapy.

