2.7. EFFICACY: SECONDARY ENDPOINT PROGRESSION FREE SURVIVAL (PFS)

2.7.1. PFS. LOCAL ASSESSMENT. ITT

Table 48. Progression-free survival at 12 and 24 weeks according to cohorts (local assessment. ITT)

Progression-free survival	N events	N patients at risk	% Estimated cumulative survival ratio	95% CI		
at 12 weeks	Cohort A					
	Cohort B					
at 24 weeks	Cohort A					
	Cohort B					
Progression-free survival	Strategy	N (%) events	Median (weeks) Min-Max	Standard error	95% CI	p-value ¹
Progression-free survival	A					
	B					
	Total					

1: Log-rank test

Figure 1. Progression-free survival according to cohorts (Local assessment ITT). Kaplan-Meier curve.

Table 49. Progression during follow-up (local assessment. ITT)

Progression-free survival	Cohort A	Cohort B	Total	p-value
PD				
Alive: Free of progression				
Total				

1: Pearson Chi-square; 2: Fisher's exact test

Table 50. Types of progressions / censorship during follow-up (local assessment. ITT)

Progression-free survival	Cohort A	Cohort B	Total	p-value
Progression-Disease progression Clinical progression				
Alive without PD at the end of follow-up				
Alive without PD: censored by surgery				
Alive without PD: abandonment due to patient decision				
Total				

1: Pearson Chi-square; 2: Fisher's exact test

GEIS-30 STUDY

Statistical analysis plan

Table 51. Time to PD (weeks) (Local assessment. ITT)

	Cohort A		Cohort B		Total		p-value ¹		
	N	Mean (SD)	Median (Min-Max)	N	Mean (SD)	Median (Min-Max)		N	Mean (SD)
Time to PD (weeks)									

1: Mann-Whitney U test

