2.7.3 PFS. CENTRAL ASSESSMENT. ITT

To describe the event in PFS, the protocol will be followed:

“Overall progression-free survival will be calculated from the date of initiation of treatment to the first date of documented progression or date of death, whatever the cause. Live patients with no evidence of progression at the time of analysis will be censored on the date of the last follow-up. ”

Table 56. Progression-free survival at 12 and 24 weeks according to cohorts (Central assessment. ITT)

Progression-free survival	N events	N patients at risk	% Estimated cumulative survival ratio	95% CI		
at 12 weeks	Cohort A					
	Cohort B					
at 24 weeks	Cohort A					
	Cohort B					
	Strategy	N (%) events	Median (weeks)	Min-Max	Standard error	p-value ¹
Progression-free survival	A					
	B					
	Total					

1: Log-rank test

Figure 3. Progression-free survival according to cohorts (Central assessment ITT). Kaplan-Meier curve.

GEIS-30 STUDY

Statistical analysis plan

Table 57. Progression during follow-up (Central assessment. ITT)

	Cohort A		Cohort B		Total	p-value
	N (% , 95% CI)		N (% , 95% CI)		N (% , 95% CI)	
Progression-free survival	PD					
	Alive: Free of progression					
	Total					

1: Pearson Chi-square; 2: Fisher's exact test

Table 58. Time to PD (weeks) (Central assessment. ITT)

	Cohort A			Cohort B			Total		p-value ¹
	N	Mean (SD)	Median (Min-Max)	N	Mean (SD)	Median (Min-Max)	N	Mean (SD)	
Time to PD (weeks)									

1: Mann-Whitney U test

Table 59. Follow-up time (weeks) (Central assessment. ITT)

	Cohort A			Cohort B			Total		p-value ¹
	N	Mean (SD)	Median (Min-Max)	N	Mean (SD)	Median (Min-Max)	N	Mean (SD)	
Follow-up time (weeks)									

1: Mann-WhitneyU test

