2.9. GMI: GROWTH MODULATION INDEX

Following the definition in the protocol, the GMI will be calculated as "the ratio between time to progression with pazopanib (TTPp) divided by time to progression with the previous line of treatment (TTPp-1)".

The time to PD with pazopanib is presented in the section EFFICIENCY: MAIN ENDPOINT and the duration of the previous chemotherapy until relapse is presented in Table 30. Number of cycles and duration of the previous chemotherapy.

Table 69. Growth modulation index (GMI) (ITT)

	Cohort A			Cohort B			Total			p-value ¹
	N	Mean (SD)	Median (Min-Max)	N	Mean (SD)	Median (Min-Max)	N	Mean (SD)	Median (Min-Max)	
Growth modulation index (GMI)										

1: Mann-Whitney U test

Table 70. Categorized GMI (ITT)

	Cohort A	Cohort B	Total	p-value
	N (%)	N (%)	N (%)	
GMI categorized				
<1				
1-1.33				
> 1.33				
Total				

1: Chi-square; 2: Fisher's exact test

Table 71. Growth modulation index (GMI) (PP)

	Cohort A			Cohort B			Total			p-value ¹
	N	Mean (SD)	Median (Min-Max)	N	Mean (SD)	Median (Min-Max)	N	Mean (SD)	Median (Min-Max)	
Growth modulation index (GMI)										

1: Mann-Whitney U test

Table 72. Categorized GMI (PP)

	Cohort A	Cohort B	Total	p-value
	N (%)	N (%)	N (%)	
GMI categorized				
<1				
1-1.33				
> 1.33				
Total				

1: Chi-square; 2: Fisher's exact test

GEIS-30 STUDY

Statistical analysis plan

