3.1.1. RESPONSE LOCAL ASSESSMENTS AND ACCORDING TO GMI. ITT

The tables below show the response to treatment at 6 and 12 weeks, based on local assessments of the TACs based on the categorized GMI variable: <1, 1-1.33 and> 3.

Table 82. Response to treatment according to GMI: Local assessment at 6 and 12 weeks ITT

		GMI categorized			p-value	
		<1	1-1.33	> 1.33		Total
		N (% , 95% CI)	N (% , 95% CI)	N (% , 95% CI)		N (% , 95% CI)
Clinical benefit at week 6 (CR, PR or SD) local	No (PD)					
	Yes					
	Total					
Clinical benefit at week 12 (CR, PR or SD) local	No (PD)					
	Yes					
	Total					

1: Chi-square; 2: Fisher's exact test

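### SAP Appendix I tests week-6/12 benefit and PFS across GMI groups that are themselves built from pazopanib progression time, so those p-values cannot show that GMI marks benefit

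*SAP*

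**What the plan says.** Protocol 10.1.2 defines the index: "GMI is the ratio between time to progression (TTP) with pazopanib (TTPp) divided by the" corresponding time on the line before. SAP 2.9 repeats it as "time to progression with pazopanib (TTPp) divided by time to progression with the previous line of treatment (TTPp-1". For the source of the numerator, SAP 2.9 says: "The time to PD with pazopanib is presented in the section EFFICIENCY: MAIN ENDPOINT". That section (2.6) holds response tables only. Time to progression is tabulated in 2.7, in two readings: "Table 51. Time to PD (weeks) (Local assessment. ITT" and "Table 58. Time to PD (weeks) (Central assessment. ITT". PFS (Protocol 10.1.2, SAP 2.7.3) runs from treatment start to progression or death.

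Appendix I announces that "the possible relationship between the main efficacy variables and the categorized GMI variables is analyzed: <1, 1-1.33 and> 3". Its tables are:

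- **Tables 82–87:** local benefit at weeks 6 and 12 by GMI group, with chi-square or Fisher p-values. The first is "Table 82. Response to treatment according to GMI: Local assessment at 6 and 12 weeks ITT".
- **Tables 88–93:** local PFS by GMI group, with log-rank p-values.
- **Tables 94–99:** OS by GMI group, with log-rank p-values.

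No alpha and no decision is attached to any of them. The SAP text available for review gives no landmark, caveat or descriptive-only label for them.

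**The concern.** A patient's week-6 and week-12 status, and in most cases the PFS date, are settled by when progression occurs on pazopanib. That same time is the numerator of GMI. A long pazopanib time therefore pushes a patient towards a higher GMI group and, at once, towards a better outcome in the table. The test in part compares a quantity with itself.

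A reader who sees a small p-value in Table 82 or Table 88 may conclude that GMI identifies patients who benefit. The p-value could be small with no such relationship, merely because progression time is on both sides. The stake is the reading of an appendix, not the trial's decision.

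**Working it through.** **1. The plan's own design figure.** Protocol 10.4 gives P0 = 20%, P1 = 40%, stop at 3 or fewer successes in 17, and a positive result at 11 or more in 37. The probability of a positive result is the sum over x from 4 to 17 of b(x; 17, p) × P(Y ≥ 11 − x), with Y binomial (20, p). This gives 0.0948 at p = 0.20 and 0.903 at p = 0.40. A search for the optimal design returns the same 3/17 and 10/37 boundaries, so the design reproduces. It never uses GMI. The documents give no design figure for the GMI analyses.

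**2. The overlap by hand.** Write GMI = T/Q, with T the pazopanib time and Q the prior-line time. Suppose every patient had Q = 16 weeks (illustrative). Progression at scans in weeks 7, 12, 20 and 28 gives GMI = 7/16 = 0.44, 12/16 = 0.75, 20/16 = 1.25 and 28/16 = 1.75. The group below 1 then contains exactly the patients who progressed by week 12. Week-12 benefit is 0% there and 100% in the other groups, whatever the drug does. Variation in Q blurs this split. Correlation between T and Q weakens it, because T/Q then says less about T.

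**3. Inputs for the size.**

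- From the documents:
  - scans at weeks 7, 12 and every 8 weeks after (Protocol 5.7), moved by up to 4 days either way (Protocol Table 5); the week-7 scan stands for the SAP's week 6;
  - a 12-week rate of 20% or 40%, the same for every patient;
  - 17, 37 or 74 patients;
  - prior-line medians of 3.3, 3.6 and 5.9 months (Protocol 4.1; a well-/dedifferentiated series only). Multiplying by 365.25/84 = 4.348 gives 14.3, 15.7 and 25.7 weeks.
- Assumed: exponential times; Gaussian-copula correlation of 0, 0.3 or 0.6; 85% of patients with a prior line.

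Under an exponential model the pazopanib median is 12 × ln 2 / (−ln p): 5.2 weeks at 20% and 9.1 weeks at 40%. Each setting used 3000–4000 simulated trials, so the simulation error is at most √(0.25/3000) = 0.9 points.

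**4. PFS log-rank, three groups, rejection at nominal 5%.**

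| Correlation | n = 17 | n = 37 | n = 74 |
|---|---|---|---|
| 0 | 14–35% | 24–60% | 41–89% |
| 0.3 | 11–18% | 11–27% | 10–45% |
| 0.6 | 11–16% | 9–22% | 8–26% |

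Permuting the GMI labels, which removes the overlap, still gives 6–13%, because the 1–1.33 group averages only 1–7 patients. The fair comparison is with that range, not with 5%. In a cohort that stops with 3 or fewer successes in 17, the figures at correlation 0 are 13–21% against 11% permuted.

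**5. Benefit tables.** For week 12, exact-test rejection at n = 17 / 37 is 9–22% / 26–52% at correlation 0, 3–9% / 8–21% at 0.3 and 1–4% / 2–6% at 0.6, against 1–5% permuted. With a true week-12 rate of 20% in every patient, the expected benefit in GMI <1 versus >1.33 is:

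- correlation 0: 11–14% versus 36–38%;
- correlation 0.3: 16–18% versus 25–27%;
- correlation 0.6: 21–22% versus 10–15%, so reversed.

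The reversal arises because the first scan puts a floor of about 7 weeks under T. A patient with Q = 4 weeks who progresses before the first scan has GMI = 7/4 = 1.75 and no benefit.

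**6. Cohort B.** Tables 92–93 print rows for <1 and 1–1.33 only. For that two-group contrast at correlation 0, two sets of simulations gave 4–11% against 5–11% permuted, and 12–15% against 6–11%: little or no excess.

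**7. Sensitivity at correlation 0 (n = 17 / 37).** A numerator from a reading that moves progression by one scan in 30% of patients gives 15–32% / 21–55%. With 15% of times censored and the censoring time used as numerator, the result is 14–30% / 22–53%. Under different scaling (pazopanib median 15.6 weeks, a prior line for everyone, fixed scan weeks, prior-line median 8–24 weeks), PFS rejection at n = 37 is 76–94%, falling to 36–72% at correlation 0.3 and 8–36% at 0.6. That median implies a 12-week rate of 0.5^(12/15.6) = 59%, above P1.

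**The case against.** The strongest reply is that this is an exploratory appendix. The SAP says only that a possible relationship is examined, and nothing is decided on it. Because GMI and these outcomes are associated by construction, a rejection is not strictly a false positive. Both points stand, and they keep the matter minor. The percentages above are not type I error rates. They show how often a small p-value appears when all patients share the same 12-week rate. Exploratory status excuses a lack of multiplicity control. It does not make the test informative when the grouping contains the outcome.

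The size is also open to attack. It rests on a correlation, a prior-line share and a prior-line median that the documents do not give for this population, and it does not carry over to Tables 92–93 as printed. This stands too, so no single figure is claimed.

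Finally, the SAP copy available for review is incomplete: it passes from the last inclusion criterion straight to Table 5. General methods text may contain a caveat, so its absence is stated only for the text available.

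A reader might infer that all 18 p-values are biased towards significance, or always in favour of high GMI. The documents do not support that. At correlation 0.6 the week-12 difference can reverse, and in many settings at 0.3–0.6 the PFS excess is small or absent.

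**Conclusion.** The circularity follows from the definition of GMI and the table shells, and needs no simulation. It affects 6 × 2 = 12 benefit p-values and six log-rank tests, 18 in all. None can serve as evidence that GMI marks benefit. With three groups, uncorrelated times and the assumed inputs, the excess is material at 37 patients. At higher correlation it may vanish or change direction. This is a minor point.

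OS by GMI has a related, weaker problem: the group is known only at progression. At correlation 0, rejection was 8–36% against 7–14% permuted, depending on the assumed survival after progression, so no size is claimed.

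Two further inferences should be resisted:

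- **That the main results are compromised.** The Simon rule does not use GMI, and the circularity does not reach the GMI summaries in Tables 69–72. What does reach those tables is a separate gap. SAP 2.9 does not say which reading supplies the numerator, or how pazopanib times without progression enter, such as "Alive without PD: censored by surgery" in Table 50.
- **That the printed 0.017 in Table 102 shows the SAP was written after the results.** It suggests that one analysis had been run. That analysis is of baseline FNCLCC grade, not efficacy, and no date is given.

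**What to change.** - **Tables 82–93:** remove the p-values and log-rank tests. If counts, confidence intervals and curves are kept, add a sentence that GMI group and these outcomes share the pazopanib progression time, so differences between groups are expected by construction and are not evidence of a GMI effect.
- **Tables 94–99:** show OS by GMI without p-values, with a note that the group is known only at progression.

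Separate minor repairs:

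- **SAP 2.9:** state whether the local or the central reading supplies the numerator, and how censored pazopanib times enter GMI. This also settles Tables 69–72.
- **GMI categories:** the text of SAP 3.1, 3.1.1, 3.1.3, 3.1.4, 3.4.1 and 3.5.1 gives the top group as >3, while the table columns use >1.33; reconcile them. Also reconcile the Cohort B rows in Tables 92–93 (no >1.33 row) and 98–99 (no 1–1.33 row) with the three stated groups.
- **Table 102:** state when the analysis behind the 0.017 was run.

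The cost is SAP text and table footers. What is lost is a set of exploratory p-values that could not answer the question.
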